7.1 Exposure to Study Treatment(s)

Treatment duration in days will be calculated as: (Date of the last treatment session – Date of the first treatment + 1) for study drugs BELKYRA and/or VOLUMA. Treatment duration will be summarized using descriptive statistics. The number of the sessions of BELKYRA and VOLUMA treatment administered over the study period will be summarized using

descriptive statistics. The total injection volume (mL) of BELKYRA and VOLUMA will be calculated and summarized, as well as treatment specific injection volumes.

Partial or missing start/end dates will be handled as per Section 3.3.3.2.

All treatment data will be listed.

7.2 Adverse Events

Adverse events (AE) will be coded using MedDRA v20.1 or later to give a PT and a SOC term for each event.

An AE is defined as any untoward medical occurrence in a clinical investigational patient administered a pharmaceutical (investigational) product or any undesirable physical, psychological or behavioral effect experienced by a subject during his/her participation in a study, in conjunction with the use of the device and which does not necessarily have to have a causal relationship with this treatment.

All AEs will be included in by-subject AE listings. A separate listing will be created with all the distinct levels of SOC and PT, and the verbatim investigator description reported in the study. Sorting will be by earliest observed SOC, PT within SOC and then verbatim description.

A treatment-emergent adverse event (TEAE) is a post-baseline AE where (i) there is no pre-treatment AE of the same MedDRA primary SOC and PT; or (ii) the maximum severity during the post-baseline period is greater than the maximal severity of any pre-treatment AE of the same MedDRA primary SOC and PT during the enrollment visit. Note that the post-baseline period of the study starts upon the initiation of the BELKYRA treatment at Visit 2.1/Day 0.

Partial or missing AE start dates will be handled as per Section 3.3.3.1.

An overall summary of frequency count and the binomial incidence rate with associated 95% CIs will be presented to describe the incidents of TEAEs. Note that 95% CIs of the binomial incidence rate will be presented for the overall summary analyses of TEAEs, but not for the by-visit analyses. Percentages and corresponding 95% CIs will be displayed to 1 decimal place.

Each type of AE will be tabulated by SOC and PT within SOC. The SOC and PT within SOC will be sorted by descending frequency. Number of subjects with percentage and number of events will be presented based on SOC and PT.

The incidence of all TEAEs by SOC and PT will be presented for the following categories:

- Any TEAE
- Any TEAE related to BELKYRA
- Any TEAE related to VOLUMA
- Any TEAE related to anesthesia
- Any TEAE related to study procedure
- Any TEAE related to BELKYRA/VOLUMA and leading to discontinuation of treatment with BELKYRA/VOLUMA
- Any TEAE by maximum severity

The following listing will be provided:

- Listing of all TEAE

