Subjects will have the option of participating in a Biopsy Sub-study. Participation in the sub-study is voluntary and will not affect the subject's eligibility to participate in the main study. Biopsy samples will be collected from the submental region at Visit B1 and B2. Samples will be collected at 2 timepoints: Visit B1 will occur at least 4 weeks before the first BELKYRA® treatment (at Visit 2.1); Visit B2 will occur 8 weeks after the last BELKYRA® treatment and at least 4 weeks prior to VOLUMA™ treatment (at Visit 4). The initial BELKYRA® treatment (Visit 2.1) will not occur until the initial biopsy site has healed (at least 4 weeks after biopsy); if not healed by 4 weeks, BELKYRA® treatment will be postponed until healed. The VOLUMA™ treatment (Visit 4) will not occur until the second biopsy site has healed (at least 4 weeks after biopsy); if not healed by 4 weeks, VOLUMA™ treatment will be postponed until healed. Histological changes from baseline to after BELKYRA® treatment(s) will be evaluated.

Data will be collected at each clinic visit for all relevant parameters per the *Schedule of Visits and Procedures (Table 1.1)*.

All adverse events (AEs) will be collected from the signing of the informed consent form (Visit 1) through to the last study visit (Visit 6). Serious adverse events (SAEs) will be reported directly to Allergan within the specified time, format, and procedure described in *Section 9: Adverse Events*. Injection site reactions (ISRs) recorded during the VOLUMA™ treatment period will be collected in an ISR Diary as described in *Section 7.1.8: Injection Site Reaction (ISR) Diary*.

Clinical Study Protocol: CMO-MA-FAS-0513

Key Criteria for Inclusion:

1. Male and females 18 to 65 years of age inclusive on the day of initial BELKYRA® treatment
2. Sign the Independent Ethics Committee (IEC)/Institutional Review Board (IRB)-approved informed consent form (ICF) prior to any study-related procedures being performed
3. Grade 2 or above on the ALJDS [REDACTED]
[REDACTED]
[REDACTED]
4. Submental fat graded by the Investigator as 2 or 3 using the CR-SMFRS [REDACTED]
[REDACTED]
[REDACTED]
5. [REDACTED]
[REDACTED]
[REDACTED]
6. [REDACTED]
[REDACTED]
7. [REDACTED]
[REDACTED]
[REDACTED]
[REDACTED]
8. [REDACTED]
[REDACTED]

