9.1.1.2 Medical Device

An AE is defined as any undesirable physical, psychological or behavioral effect experienced by a subject during his/her participation in a study, in conjunction with the use of the device, whether or not it is considered related to the procedure or the product. AEs may include, but are not limited to, subjective or objective symptoms spontaneously offered by the subject, solicited via subject interviews, uncovered by review of concomitant medications, therapies, and treatments and/or observed by the Investigator. The Investigator will record the description (sign, symptom and diagnosis), location, onset, resolution, seriousness, severity, cause, and action taken for any event on the AE eCRF. To maintain study blind, the Evaluating Investigator must not be present during the safety evaluations.

Disease signs and symptoms that existed prior to the study injections are not considered AEs unless the condition recurs after the subject has recovered from the pre-existing condition or the condition worsens in intensity or frequency during the study.

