3.1 Analysis Populations

To adequately describe the statistical analyses, three analysis populations are defined as follows:

- Full Analysis Set (FAS): Consists of all subjects who received BELKYRA.
- Evaluable Set (ES): Consists of the FAS subjects who received both BELKYRA and VOLUMA and a post-treatment efficacy assessment at Visit 6 (Exit Visit).
- Safety Analysis Set (SAS): Consists of all subjects who consented to participation. Includes subjects who are defined as FAS subjects and those subjects who underwent biopsy procedure but did not receive the BELKYRA treatment. This population will be used for safety analyses.

Unless specified otherwise, the FAS will be used for summary of subject disposition, demographics, baseline characteristics, and for efficacy analyses of endpoints that are

assessed up to the end of BELKYRA treatment; the Evaluable Set will be used for the efficacy analyses of endpoints that are assessed at the final study visit, and the Safety Analysis Set will be used for safety analyses.

Note that in the context of the SAP (including the TFL mockup shells), subjects in the safety analysis set are called safety subjects, and subjects in the evaluable set are called evaluable subjects. Also, the terms of full analysis set, safety analysis set and evaluable set mentioned in the protocol are used interchangeably with full analysis population, safety analysis population and evaluable population respectively.

[REDACTED]

[REDACTED]

[REDACTED]

[REDACTED]

[REDACTED]

[REDACTED]

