3.3.3.1 For assigning treatment-emergent AEs (TEAEs), and prior and concomitant medications

The followings rules will be applied for partial or missing start dates:

- If the day is missing, the first day of the given month will be used unless the month and year are the same as the month and year of enrollment, in which case the date of enrollment will be used. Note that the enrollment date for the subjects of the biopsy sub-study is at Visit B1, instead of Visit 2.1.
- If the day and month are missing, the 1st of January will be used unless the year is the same as the year of enrollment, in which case the date of enrollment will be used.
- If the whole date is missing, the date of enrollment will be used.

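### SAP 7.2 lets a resolved pre-treatment AE, such as a healed first-biopsy reaction, stop an equal or milder later event of the same preferred term from counting as treatment-emergent, and tabulates no first-biopsy events

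*SAP*

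**What the plan says.** SAP 7.2 defines a TEAE as a post-baseline AE that meets either of two limbs. The first reads "i) there is no pre-treatment AE of the same MedDRA primary SOC and PT". The second is met when "the maximum severity during the post-baseline period is greater than the maximal severity of any pre-treatment AE" of the same term, and it closes with the words "SOC and PT during the enrollment visit". The SAP adds that "the post-baseline period of the study starts upon the initiation of the BELKYRA treatment at Visit 2.1/Day 0". For sub-study subjects, SAP 3.3.3.1 states that "the enrollment date for the subjects of the biopsy sub-study is at Visit B1, instead of Visit 2.1".

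The Protocol Summary says of the sub-study: "The initial BELKYRA® treatment (Visit 2.1) will not occur until the initial biopsy site has healed". The interval from biopsy to treatment is at least 4 weeks.

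The device AE definition in Protocol 9.1.1.2 says that pre-existing signs and symptoms are not AEs "unless the condition recurs after the subject has recovered from the pre-existing condition", or the condition worsens.

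Every AE category listed in SAP 7.2 is a TEAE category, and SAP 7.3 tabulates treatment-emergent SAEs. The Safety Analysis Set in SAP 3.1 "Includes subjects who are defined as FAS subjects and those subjects who underwent biopsy procedure but did not receive the BELKYRA treatment", and SAP 7 uses the safety population as the incidence denominator. SAP 7.2 also places all AEs in by-subject listings.

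**The concern.** The usual purpose of a treatment-emergent rule is to exclude conditions that were already present when treatment began. This rule also excludes conditions that had been present and had gone. In most of this trial that hardly matters, because subjects outside the sub-study have no study procedure before Day 0 that would cause local reactions. Sub-study subjects do: tissue is excised from the submental area, the site heals, and BELKYRA is then injected into the same area. Local reactions to the two may well be coded to the same PT.

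Two things are at stake. First, reactions that occur on treatment can go uncounted in the PT rows. Second, complications of the first biopsy, a research procedure done for this study, have no place in the listed incidence categories. Subjects who are biopsied and then withdraw, whom Protocol 6.1.4 anticipates, sit in the denominator but can never supply a TEAE.

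**Working it through.** The plan has no figure to reproduce here. Its only sizing calculation (Protocol 10.7) concerns the ALJDS responder rate, and no AE rate is stated anywhere. The check therefore applies the rule to each case and then bounds the effect.

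**1. Where first-biopsy events fall.** AEs are collected from consent (Protocol 9). Post-baseline starts at first BELKYRA (SAP 7.2). Every event between Visit B1 and Visit 2.1 is therefore pre-treatment, even if it has resolved.

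**2. The rule applied to a PT that occurs both before and after Day 0.** Limb (i) fails, so only limb (ii) can count it. This table reads limb (ii) as comparing with any pre-treatment AE of that PT:

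| Worst severity before Day 0 | Post-baseline maximum mild | moderate | severe |
|---|---|---|---|
| mild | not counted | counted | counted |
| moderate | not counted | not counted | counted |
| severe | not counted | not counted | not counted |

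Six of the 9 combinations are not counted: all those with equal or lower severity afterwards. These are cells of the rule, not probabilities. Limb (ii) uses the maximum over the whole post-baseline period, so one worse occurrence at any later time satisfies it.

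**3. The enrollment-visit wording.** For sub-study subjects the enrollment date is at Visit B1. If the qualifier restricts the severity comparator to events at that visit, an event arising days later leaves the comparator empty. The later event might then count, or limb (ii) might be impossible to evaluate while limb (i) still fails. The text does not settle which.

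**4. The second biopsy.** Visit B2 comes 8 weeks after the last BELKYRA treatment and is post-baseline. A B2 reaction can enter the category for TEAEs related to study procedure, unless the same PT occurred after B1 at equal or greater severity.

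**5. Size for one PT.** Inputs: 50 treated subjects, 10 of them biopsied (SAP 1), so the exposed share is 10/50 = 0.2. Assumptions: *t* is the true post-BELKYRA incidence, equal in biopsied and other subjects. *s* is the share of affected biopsied subjects who had the same PT before Day 0 at equal or greater severity.

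Reported incidence = *t* × (1 − 0.2 × *s*)

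| *t* | *s* = 0 | *s* = 0.5 | *s* = 1 |
|---|---|---|---|
| 20% | 10/50 = 20% | 9/50 = 18% | 8/50 = 16% |
| 50% | 25/50 = 50% | 45% (expected 22.5/50) | 20/50 = 40% |
| 80% | 40/50 = 80% | 36/50 = 72% | 32/50 = 64% |
| 100% | 50/50 = 100% | 45/50 = 90% | 40/50 = 80% |

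The pooled loss for one PT runs from 0 to 10 of 50 subjects (20 points). Within the sub-study it can be total: at *t* = 80% and *s* = 1, 8/10 becomes 0/10.

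**6. B1-to-Day-0 events.** If *k* of 10 biopsied subjects have such an event, the listed TEAE and treatment-emergent SAE categories show 0 of them whatever *k* is. A table restricted to biopsied subjects would show *k*/10. For *k* = 3 that is 30%, exact 95% CI 6.7% to 65.2%.

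**The case against.** The strongest reply is that the effect is small and nothing is hidden. The rule works by PT, so a subject with one blocked term still counts in the any-TEAE and BELKYRA-related rows through any other qualifying term. About 40 of 50 subjects have no B1 visit. The biopsy is about 2 mm (Protocol 7.1.7), against up to 50 injections and 10 mL per treatment for up to six treatments (Protocol 5.1.1), so a later event will often be the more severe and pass limb (ii). All AEs are listed by subject, and with about 10 biopsied subjects a reader can inspect each one. The VOLUMA diary tables (SAP 7.4) do not use the TEAE rule. All of this stands, and it makes the upper end of the range unlikely.

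The reply also has force on two further points. The recurrence wording in Protocol 9.1.1.2 says what is an AE, and it sits in the device subsection, whereas BELKYRA is the drug. The SAP does not deny that a recurrence is an AE, so this is a mismatch to reconcile rather than a direct contradiction. In addition, SAP 7.2 has a general sentence about tabulating each type of AE, and Protocol 10.5.5 presents AEs with TEAEs summarized in addition. A reader might infer that first-biopsy events are kept out of every table. The text supports only that they enter none of the listed categories.

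The reply does not remove the defect. A listing gives no incidence, a resolved event still blocks a later one, and the enrollment-visit wording still allows two different safety tables from the same data.

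**Conclusion.** The point holds as a defect in the TEAE definition, of modest size. Under SAP 7.2 an event after BELKYRA, or after the second biopsy, is not counted in its PT row when the same term occurred before treatment at equal or greater severity, even if it had fully resolved. For events arising after the B1 visit but before Day 0, that depends on how the enrollment-visit wording is read. The pooled loss for any one PT is 0 to 20 percentage points. It rests on assumed incidence and overlap, because the documents give neither, and it falls to 0 if the biopsy and BELKYRA reactions are coded to different terms. AEs and SAEs with onset between B1 and Day 0 enter no listed TEAE or treatment-emergent SAE category.

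Two stronger readings should be avoided. A reader might infer that about 20% of subjects lose their reactions. That figure is the share exposed to the rule (10 of 50), and it becomes the loss only if all 10 have the matching event before and after. A reader might also infer that an affected subject disappears from the overall TEAE count. That happens only when no other term qualifies.

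**What to change.** In SAP 7.2 and 7.3:

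- Define a TEAE as an AE with onset on or after the first BELKYRA injection, or an AE ongoing at that time that later worsens.
- Delete the enrollment-visit qualifier.
- State that a resolved pre-treatment AE does not block a later event, which also brings the rule into line with the recurrence wording in Protocol 9.1.1.2.
- Add one table of AEs and SAEs with onset from the B1 biopsy to before first BELKYRA, with all biopsied subjects, treated or not, as the denominator.

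The cost is a SAP amendment before database lock and one short table. No new data are needed, since onset, resolution and severity are among the items that Protocol 9.1.1.2 has recorded on the AE form. TEAE rates may become slightly less favourable, and the new table will be imprecise with about 10 subjects.

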5.1.3 Blinding and Randomization

This is an open-label, single-arm study. Thus, blinding and randomization methods will not be implemented.

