9.1.5 Relationship to Study Medication or Study Device

A determination will be made, by the Investigator, of the relationship (if any) between an AE and the study drug, anesthesia employed, the study device, or the injection procedure, as applicable. A causal relationship is present if a determination is made that there is a reasonable possibility that the AE may have been caused by the drug, device, or study procedure.

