10.5.5 Adverse Events

AEs will be coded using MedDRA version 17.0 or higher, and presented by system organ class and preferred term. Treatment-emergent AEs will also be summarized by SAEs, AE severity, AE leading to treatment or study early termination, and relationship to study drugs/devices. Summary tables will be presented by the study treatment drug.

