7.3 Serious Adverse Events

A serious adverse event (SAE) is any AE occurring at any dose that results in any of the following outcomes: death, a life-threatening AE, inpatient hospitalization or prolongation of existing hospitalization, a persistent or significant disability/incapacity, or a congenital anomaly/birth defect. While an unanticipated adverse device effect (UADE) is any device-related SAE that meets one or more of the criteria listed in the Sec. 9.1.3 of the Protocol in page 49.

An overall summary of frequency count and the binomial incidence rate with associated 95% CIs will be presented to describe the incidents of treatment emergent SAEs. Note that 95% CIs presented are for the overall summary analyses of SAE, but not for the by-visit analyses. Percentages and corresponding 95% CIs will be displayed to 1 decimal place.

The incidence of all treatment-emergent SAEs by SOC and PT within SOC will be presented for the following categories:

- Any SAE
- Any SAE related to BELKYRA
- Any SAE related to VOLUMA
- Any SAE related to anesthesia
- Any SAE related to study procedure

- Any SAE related to BELKYRA/VOLUMA treatment and leading to discontinuation of treatment
- Any SAE by maximum severity

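### Apart from the diary reaction table, no defined SAP table shows adverse events by onset after VOLUMA among VOLUMA-treated subjects, and VOLUMA rates use the whole safety set as denominator

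*SAP*

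**What the plan says.** Protocol 10.5.5 states: "Summary tables will be presented by the study treatment drug". It does not say whether the split is by attribution or by the time an event began.

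SAP 7.2 fixes the period: "Note that the post-baseline period of the study starts upon the initiation of the BELKYRA treatment at Visit 2.1/Day 0". Visit 4, the first VOLUMA injection, is not a second reference point. An event is treatment-emergent if no pre-treatment event had the same system organ class and preferred term, or if its worst post-baseline severity is "greater than the maximal severity of any pre-treatment AE of the same MedDRA primary SOC and PT during the enrollment visit".

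The tables are introduced by "The incidence of all TEAEs by SOC and PT will be presented for the following categories". The list covers any TEAE; TEAEs related to BELKYRA, VOLUMA, anesthesia or procedure; related TEAEs leading to discontinuation; and maximum severity. The only VOLUMA entry defined by product alone is "Any TEAE related to VOLUMA". SAP 7.3 repeats the scheme for serious events, with "Any SAE related to VOLUMA".

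Attribution belongs to the Investigator. Protocol 9.1.5: "A determination will be made, by the Investigator, of the relationship (if any) between an AE and the study drug". Protocol 5.1.3: "This is an open-label, single-arm study. Thus, blinding and randomization methods will not be implemented".

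The opening of SAP 7 counts a subject once per summarization level and divides by the number in the safety population. SAP 3.1 defines that population as all consenting subjects.

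**The concern.** Protocol 1.2 makes the safety of the sequence part of the rationale. On efficacy, SAP 6 separates the steps: change to Visit 4 describes BELKYRA, and change to Visit 6 describes the combination. No matching split is defined for adverse events.

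A reader of the study report will want to know which events began, came back or got worse once filler was added, in what share of those who received it. The attribution tables cannot give this, because they omit any event after VOLUMA that the Investigator assigns to BELKYRA or to neither product. The all-causality tables cannot give it either, because they cover both steps at once. Whatever VOLUMA rate is reported is also divided by a group that includes subjects who never had VOLUMA.

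**Working it through.** **Step 1: follow one hypothetical subject through the tables.** The subject has no pre-treatment headache, a mild headache after BELKYRA, and a moderate headache after VOLUMA that the Investigator judges unrelated to either product.

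- Any TEAE, subject count: 1, the same as without the second headache.
- Any TEAE, event count: 2, with nothing to show when either began.
- Related to VOLUMA: not counted.
- Maximum severity: moves from mild to moderate, with nothing to show that this followed VOLUMA.
- By-subject listing: both events appear, without a rate.
- Diary table (SAP 7.4): not counted, unless the subject enters it as an injection site reaction.

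The second event is therefore recorded, but no defined summary identifies it as emerging on VOLUMA.

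**Step 2: the plan's own loss figure.** Protocol 10.7 needs 40 subjects and allows 20% for drop-out and/or not continuing to VOLUMA: 40 / (1 − 0.20) = 50. This reproduces the stated enrolment.

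**Step 3: effect of the denominator.** Let V be the number given VOLUMA, N the safety set and x the number affected. The reported rate is x/N and the rate among those exposed is x/V, so reported/exposed = V/N.

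V is not stated. I assume 40 to 50, because some of the 20% may leave after receiving VOLUMA. N is at least the number treated (50). It is larger if consenting but untreated subjects are included; 55 is an assumed example.

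| V | N | V/N | x = 4, exposed | x = 4, reported |
|---|---|---|---|---|
| 40 | 50 | 0.80 | 10.0% | 8.0% |
| 40 | 55 | 0.73 | 10.0% | 7.3% |
| 45 | 50 | 0.90 | 8.9% | 8.0% |
| 50 | 50 | 1.00 | 8.0% | 8.0% |

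Exact (Clopper-Pearson) 95% intervals:

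- 4/40: 2.8% to 23.7%
- 4/50: 2.2% to 19.2%
- 4/55: 2.0% to 17.6%

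With no events, the upper limit is 8.8% for n = 40 and 7.1% for n = 50, so the larger denominator also makes a zero look more reassuring than the exposure supports.

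**Step 4: effect of counting once.** Suppose a non-diary term affects 10% of 40 VOLUMA-treated subjects after VOLUMA: 40 × 0.10 = 4. If a share p already had it after BELKYRA, independently, then 4p of these add nothing to the pooled subject count: 0.4 at p = 10% and 1.2 at p = 30%. These rates are assumptions that show the mechanism; the documents give none.

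**The case against.** The strongest reply is that VOLUMA safety is already covered. SAP 7.4 tabulates diary reactions after VOLUMA by preferred term, with subjects, events and exact intervals. Protocol 7.1.8 and 9.1.1.3 show that these are subject-reported, daily for four weeks after the last VOLUMA treatment, and cover the expected local reactions. That table depends on timing and needs no causality judgement. SAP 7.2 also gives event counts and listings, which can be read through in a study of about 50. This stands, and it rules out the inference that events after VOLUMA cannot be seen. It does not reach serious events or adverse events outside the diary, and listings and pooled event counts supply no rate for the VOLUMA phase.

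Second, a reader might infer that the SAP breaks the protocol's commitment to tables by study drug. The documents do not support that. Tables by relationship to each product are one reasonable reading of the sentence, and SAP 1 gives the SAP precedence over the protocol's statistics section. This is a gap, not a contradiction.

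Third, SAP 7 speaks of incidence within a given period, and SAP 7.2 and 7.3 mention by-visit analyses. These could separate the phases, but the available text does not define them. The table shells mentioned in SAP 3.1 are not available, and some SAP text is redacted, so the finding concerns what is defined in the text.

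Fourth, SAP 3.3.5 makes subjects at risk the default denominator. It does so unless otherwise specified, and SAP 7 specifies the safety population.

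Finally, a reader might suppose that causality is judged by the person who injected both products. The documents do not say so. The point needs only that the Investigator judges it without blinding.

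**Conclusion.** The point holds for adverse events other than diary reactions, and for all serious events: no defined table gives incidence by onset after first VOLUMA among those treated with it, and emergence is never re-based at Visit 4. An event that recurs or worsens after VOLUMA is left to pooled event counts, the maximum-severity table and listings, unless the Investigator attributes it to VOLUMA.

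The denominator understates VOLUMA rates by the factor V/N. That is 0.80 if 40 of 50 treated subjects receive VOLUMA, lower if the safety set includes untreated subjects, and 1.00 if every safety-set subject receives VOLUMA. Under the general rule in SAP 7 the same dilution applies to the VOLUMA-related and diary rates. The split is assumed from the 20% allowance in Protocol 10.7. The primary efficacy result is not affected.

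**What to change.** In SAP 7.2 and 7.3, add TEAE and SAE tables by onset phase:

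- **BELKYRA phase:** from Day 0 to before the Visit 4 injection, or to exit for subjects who leave without VOLUMA. The denominator is BELKYRA-treated subjects.
- **VOLUMA phase:** from the Visit 4 injection to exit. The denominator is VOLUMA-treated subjects. Count events that start, recur or worsen relative to status at Visit 4.

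Use the VOLUMA-treated denominator for the VOLUMA-related TEAE and SAE rates and for the diary rates in SAP 7.4. Keep the tables by relationship. Define the by-visit analyses or delete the references to them.

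Two details need a sentence each. SAP 3.3.3.1 sets a missing onset day to the first of the month, which would usually place an event from the month of Visit 4 in the BELKYRA phase, so state a rule for such dates. State also how worsening is identified. If the case report form keeps only one severity per event, worsening across Visit 4 cannot be derived and the table should say so.

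The cost is SAP wording, one derived phase variable and a repeat of existing tables. Protocol 9.1.1.2 already has onset recorded, and SAP 7.1 uses treatment dates, so study conduct does not change. If the database is already locked, SAP 1 allows the tables to be reported as additional analyses in the clinical study report.
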